1. CLINICAL PROTOCOL

1.1 Background

The cornea is an optically clear tissue that can become opaque as the result of a variety of pathological conditions. Most conditions can be treated with a cadaveric cornea transplant. However, under some pathological conditions, such as autoimmune diseases (Steven Johnson Syndrome, Ocular Cicatricial Pemphigoid, Rheumatoid Arthritis), and previous cornea transplant graft failure, repeat corneal transplants have a very poor likelihood of success.

Additionally, due to the changes in survival, munitions, and style of warfare, the proportion of surviving soldiers with serious anterior segment eye trauma has progressively escalated over the last century. According to Veterans Affairs (VA) data, eye trauma accounted for 15% of all battlefield injuries during Operation Iraqi Freedom and Operation Enduring Freedom, resulting in over 186,000 eye injuries in American soldiers between 2000 and 2010. These soldiers and veterans with devastating corneal injuries and autoimmune disorders associated with traumatic and degenerative changes of the cornea also have a very poor likelihood of cornea transplant success.

In these high risk patient populations, a keratoprosthesis (artificial cornea) is used. The Boston keratoprosthesis (Boston KPro) is an artificial cornea developed at the Massachusetts Eye and Ear Infirmary under the leadership of [name]. It was FDA-approved in 1992 for use in subjects with repeated corneal graft failures, ocular chemical burns, autoimmune and cicatrizing diseases, aniridia and ocular herpetic infections. This increasingly popular prosthesis has helped restore vision to thousands of subjects who otherwise had no other viable alternatives. However, despite the modifications made to improve the Boston KPro over the years, some of these keratoprosthesis subjects go on to develop sterile ulcerations and thinning of the cornea tissue which acts as a carrier for the keratoprosthesis. This corneal melting (keratolysis) of the donor cornea still remains a rare yet devastating post-operative complication that leads to exposure to pathogens, perforation, leakage of the aqueous humor and extrusion of the keratoprosthesis.

While bench-top studies and small case series have suggested that corneal melts can be reduced by collagen cross-linking the donor cornea, a prospective, randomized, multicenter, double-masked, vehicle-controlled study is needed to evaluate the safety and efficacy of cross-linking of the keratoprosthesis carrier cornea.

1.2 Rationale

The experimental drug for this trial is riboflavin (vitamin B2) 0.1% solution and dextran 20% solution. The medication includes a formula that is applied topically to the cornea while the tissue is exposed to UV light. The riboflavin reduces the intensity of the UV light that penetrates the cornea by 95%.

Cross-linking is a term that refers to the linking of polymers (long chain) molecules by chemical bonds. It is commonly performed in industry when manufacturing synthetic materials.

Biologically, cross-linking has been used to modify or strengthen tissue such as porcine valves used in heart surgery. Corneal cross-linking was first suggested in Germany in the 1990s. Since the cornea is predominantly made of long structural proteins called collagen, it was theorized that cross-linking the collagen should make the cornea stronger and resistant to degradation. The combined use of ultraviolet A light and riboflavin (as a photosensitizer) was shown to be a simple and effective cross-linking technique. Animal studies have shown this method to be safe. In addition, researchers found cross-linked corneas to be highly resistant to enzymatic degradation.

Human clinical trials have been conducted in Europe for the use of riboflavin/UVA corneal cross-linking in subjects with ocular diseases that involve corneal thinning such as keratoconus. Such trials are currently underway in the United States. There are many published reports demonstrating the safety of this method in humans. The Massachusetts Eye and Ear Infirmary has been approved to join one of the multi-center study trials using the Caporossi-Baiocchi-Mazzotta (CBM) VEGA X-linker). The goal of our study is to use the same protocol designed for that study for our study. The exception is that the corneal cross-linking of the donor corneal tissue will be performed ex-vivo prior to the Boston KPro assembly. The Boston KPro assembly will otherwise remain unchanged and the patient will not be exposed to the UVA light.

Unfortunately, there are no good animal models to test our technique with the Boston KPro. Rabbits are poor models since their clinical results have notoriously poor correlations with human clinical outcomes.

Initially, we worked on determining the optimal riboflavin/UVA cross-linking method to increase resistance of the corneas to enzymatic degradation ex-vivo.

The methodology was as follows. The corneal epithelia from the enucleated eyes of mature white New Zealand rabbits were mechanically removed using a 57 blade. The corneas with 2-3mm scleral rims were excised and their irises were removed. They were fitted into Barron® artificial anterior chambers with the endothelium bathed in isotonic saline solution. The VEGA® LED-based UVA emitter was switched on for at least 30 minutes prior to calibration then was calibrated before the experiments. The corneas were then pre-treated with 0.1% riboflavin/20% dextran T500 every 2-3 minutes for 15 minutes followed by UVA light ($\lambda = 370\text{nm}$, irradiation = 3mW/cm²) at a fixed distance of 54mm from the top of the corneas for 5-minute intervals, while applying riboflavin between irradiations. Either the anterior stroma (A) or the anterior (A) and posterior stroma (P) was irradiated for different durations (7.5A, 7.5A/7.5P, 15A, 15A/15P, 30A, 30A/30P and 60A minutes). The primary control was no riboflavin/no UVA. Secondary controls included riboflavin/no UVA and UVA/no riboflavin. The corneas were trephined into 8.5-mm buttons and incubated in clean glass vials containing 0.3% collagenase A solutions at 37°C and rotating at 150 rotations-per-minute. The time to total dissolution of the corneas was measured. Each group included 4 or more corneas.

Results showed that the primary control dissolved at 4.8h ± 0.8 while tissue cross-linked for 15 minutes dissolved after 50.0 ± 8.1 hours. Compared to the control, there was a marked increase in resistance to degradation for all UVA/riboflavin cross-linked corneas. In general, anterior stromal cross-linking was superior to anterior/posterior stromal cross-linking (whether the irradiation time was split or doubled between the anterior and posterior stromata compared to their matched groups of anteriorly cross-linked corneas). The minimal treatment that yielded the greatest resistance in all groups was 15 minutes of anterior stromal cross-linking (50.0h $\square 8.1$; $p < 0.0001$). The results were similar for 15, 30, and 60 minutes of cross-linking. Therefore, we identified several methods to increase the corneal resistance to enzymatic degradation using the corneal cross-linking technique.

The UVA emitter emits constant irradiation energy of 3mW/cm² that requires the UVA light source to be at 54mm from the cross-linked cornea. The irradiated area can be controlled using

This study's population will include subjects who are both candidates for a Boston KPro and had either a history of corneal melting (keratolysis) or have high risk for corneal melting. Boston KPro candidates include subjects with visual loss due to corneal scarring that are not candidates for a traditional corneal transplant. Typically, these subjects have either failed a corneal transplant or have ocular findings that strongly predict a very high likelihood of cornea transplant failure (e.g. subjects with extensive neovascularization of the cornea). Subjects at high risk for corneal melt include, but are not limited to, those with underlying autoimmune diseases such as ocular cicatricial pemphigoid, Stevens Johnson Syndrome, rheumatoid arthritis, lupus, and others. We are aiming to enroll 84 subjects, male or female, ages greater than 18, who are

otherwise healthy enough to undergo an elective procedure such as a corneal transplant. More information on the specific inclusion and exclusion criteria can be found in section 4 below.

Accumulating experimental data and the fact that collagen crosslinked cornea tissue resists enzymatic digestion suggest that crosslinked cornea tissue may resist the sterile cornea ulcers that develop in keratoprosthesis subjects. This approach would be a significant step forward in addressing the need for an improved treatment modality in this desperate patient population.

Riboflavin and UV light are used and marketed outside most of the United States for the treatment of corneal ectasias (keratoconus), but not for this purpose of preventing corneal melts. To our knowledge, the drugs and devices have not been withdrawn from any research or market due to reasons related to safety or efficacy.

2. STUDY OBJECTIVES

2.1 Primary Objective

This is a phase I/II prospective, randomized, multicenter, double-masked, vehicle-controlled clinical trial evaluating the safety and efficacy of corneal collagen cross-linking the keratoprosthesis carrier tissue in subjects who are candidates for high-risk keratoprosthesis implantation because of a history of corneal melts, sterile corneal ulcers, or autoimmune diseases (e.g., Stevens-Johnson syndrome, ocular cicatricial pemphigoid).

Objective 1:

Determine the safety of using a collagen cross-linked cornea as a carrier for the Boston Keratoprosthesis in subjects who are at high risk for corneal melts and are not candidates for a standard corneal transplant.

Objective 2:

Determine the efficacy of using a collagen cross-linked cornea as a carrier for the Boston Keratoprosthesis in preventing corneal melts and increasing the retention of the keratoprosthesis. This will be tested using the outcome measures listed in section 10.

2.2 Secondary Objective(s):

N/A

3. STUDY DESIGN

3.1 Study Design Description

The study is a multi-center, parallel, randomized, double-blinded study with a subsequent follow-up period of 2 years (week 52) and standard of care follow up every 6 months for an additional 3 years or until study closure to collect event data. Once a patient has been identified as a potential study participant who informed consent for this study will be obtained and eligibility will be confirmed. When a screened participant meets the inclusion and exclusion criteria to be enrolled in the study, the investigator will request a cadaveric cornea from CorneaGen (previously KeraLink International) the central eye bank for this study. The eye bank will assign the subject the next available subject (randomization) number, in ascending sequential order according to the block schedule until all assignments have been used. The eye bank will then prepare the cadaveric cornea according to one of following two randomization groups in equal allocations:

Group 1: Active Treatment Arm

De-epithelialized corneas will be cross-linked with riboflavin 0.1% with dextran 20% AND ultraviolet A light.

Group 2: Control Treatment Arm

- De-epithelialized corneas will be exposed to only riboflavin 0.1% with dextran 20% (NO ultraviolet A light).

As detailed in section 5, both the treatment arm and control arm corneas will be labeled with their unique randomized identification number in a sealed bottle of OptiZol® solution, as per the standard of care for cornea donor preservation. The tissue bank will follow their standard operating procedures for the packaging and shipment of the tissue. The masked corneas will be sent to the masked investigators, who will perform the assembly and implantation of the Boston Keratoprosthesis. The procedure will be unchanged from a typical Keratoprosthesis assembly and insertion (see study procedures in section 7).

Subjects will be followed up post-operatively by the site investigators as standard for this procedure. This will include visits at Day 1, Weeks 1, 4, 16, 24, 36, and 52, . Subjects following Boston KPro surgery are typically seen every 6months after one year follow-up. However, some may need to be seen more regularly if they require more frequent monitoring for conditions such as glaucoma. The investigators will monitor for systemic and ocular adverse events at all follow-up visits. All adverse events will be reported to the principal investigator and Medical Monitor; and then to the MEEI HSC, sub-sites, DOD, and FDA per the specified guidelines.

4.2 Allocation/Randomization to Treatment

Eighty-four subjects will be randomized equally to treatment or control group. Randomization will be stratified by 16 centers, as well as two pre-operative diagnostic categories: autoimmune disease vs. prior corneal melt without autoimmune disease. Thus there will be a total of 32 strata. Stratification will ensure balance of the stratification factors between the two arms of the study. A number of blocks of varying size will be determined (e.g. 5 blocks of size 4, 6 blocks of size 2) and randomization assignments will be prepared accordingly. Since we have 32 strata, relatively small block sizes will be planned to minimize the chance of large departures from the desired allocation ratio that could occur due to incomplete blocks by the time of completion of patient recruitment. Although the ability of the clinical staff to predict future treatment assignments is increased due to smaller block sizes, we do not think that this will be a major issue for the present study.

The study statistician at Mass Eye and Ear will prepare the computer-generated randomization schedules and treatment strata prior to commencement of the study. Codes will be used to label different treatment assignments so study site personnel will be blinded to treatment allocation. The randomization schedule will be determined in 4 steps: 1) arrange the initial treatment assignments arbitrarily, 2) generate via computer a list of pseudorandom numbers, 3) link the initial treatment codes with the pseudorandom numbers, 4) order the pseudorandom numbers from smallest to largest with associated treatment codes to determine the final order of treatment assignments. The final treatment order and strata will be communicated by the MEE unblinded study staff directly to CorneaGen prior to study start up.

4.2.1 Masking Procedures

When a participant is enrolled into the study, the Coordinator at each site will request a cadaveric cornea from CorneaGen for each eligible subject. The eye bank will use the

randomization schedules according to the stratum of the patient (center and autoimmune disease status) and assign the subject the next treatment available. Each consecutive patient who falls into the same stratum will be assigned the next treatment assignment on this sheet until all assignments have been used. Whenever a patient is enrolled who falls into a stratum for which no sheets have been started or for which all previous sheets have been completed, the next sheet will be used according to the appropriate stratum, and so on. After the tissue is prepared, it will be sent to the site in a bottle labeled with the subject's identification number.

4.2.2 Breaking the Mask

In the event of an emergency, the investigator can call CorneaGen to unmask the study treatment for an individual subject.

5. SUBJECT SELECTION

5.1 Subject Inclusion Criteria

The eligibility criteria must be met at the screening visit, and relevant medical and non-medical conditions will be taken into consideration when deciding whether this protocol is suitable for a particular subject. Subjects will be screened using the following inclusion and exclusion criteria, which are designed to select subjects for whom the protocol treatment is considered appropriate:

- Willing and able to provide written informed consent
- Willing and able to comply with study assessments for the full duration of the study
- Age \geq 18 years
- Candidate for a Boston Keratoprosthesis / Cornea transplant
- Subjects with an eye at risk for a cornea sterile ulcer which includes:
 - Autoimmune diseases (mucus membrane pemphigoid, Stevens-Johnson syndrome, systemic lupus erythematosus, and rheumatoid arthritis)

OR

- History of previous sterile cornea ulceration

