### Inclusion Criteria:

Previous sterile corneal ulceration	56
Autoimmune disease (ocular or other)	15
Ocular Cicatricial Pemphigoid	1
Steven Johnson's syndrome	7
Rheumatoid Arthritis	4
GVHD	2
Vogt-Koyanagi-Harada	1
Both autoimmune disease and previous ulceration	4
No autoimmune disease or previous ulceration	1

\*Will include this subject for safety analysis but will remove for efficacy analysis

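### The SAP removes one randomized eye from efficacy despite its intent-to-treat rule, and counts as autoimmune three subjects whose disease Protocol 5.1 does not name

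*Protocol*

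**What the plan says.** **Eligibility.** Protocol 5.1 introduces the risk criterion with "Subjects with an eye at risk for a cornea sterile ulcer which includes" and then gives two alternatives. The first is "Autoimmune diseases (mucus membrane pemphigoid, Stevens-Johnson syndrome, systemic lupus erythematosus, and rheumatoid arthritis", closed by a bracket with no wording such as 'for example'. The second is "History of previous sterile cornea ulceration". Either one suffices.

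**Population described elsewhere.** Protocol 1.2 is openly non-exhaustive: "Subjects at high risk for corneal melt include, but are not limited to, those with underlying autoimmune diseases such as ocular cicatricial pemphigoid". Protocol 2.1 likewise gives autoimmune diseases as examples.

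**Stratification.** Protocol 4.2 and 11.3 stratify by centre and by two diagnostic categories: autoimmune disease, or an earlier melt with no autoimmune disease. Protocol 4.2.1 has the eye bank use "randomization schedules according to the stratum of the patient (center and autoimmune disease status". None of these sections lists the diseases that count.

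**SAP counts.** The Inclusion Criteria table covers autoimmune disease of the eye or elsewhere and counts 15 subjects. They include 2 with GVHD and 1 with "Vogt-Koyanagi-Harada". One further subject has neither qualifying condition, and the footnote reads "Will include this subject for safety analysis but will remove for efficacy analysis".

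**Analysis set.** The SAP's Primary Analysis, like Protocol 11.5, commits the primary efficacy analysis to intent-to-treat over every eye randomized. Protocol 11.4 (Analysis Population) is marked not applicable, so no other efficacy set is defined.

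**The concern.** There are two linked problems.

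First, the SAP promises an analysis of every randomized eye and then takes one out of efficacy. The eye bank assigns the randomization number before the tissue is prepared (Protocol 3.1), so an implanted study eye is a randomized eye. The exclusion appears in a document whose opening results already give 20 removals among 68 KPros. An exclusion first written once events are known needs a stated and uniform basis, and the SAP states none.

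Second, the eligibility rule that the SAP applies in making that exclusion is not the one worded in 5.1. Three subjects count as autoimmune through diseases that 5.1 does not name. If the trial is to single out subjects who did not meet the entry criteria, the criteria used must be the protocol's, and the same check must be made for everyone. Otherwise the efficacy set rests on a reading of the criterion recorded only after enrolment.

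**Working it through.** **Inputs** (SAP, Inclusion Criteria table and Preliminary Results): previous ulceration 56; autoimmune 15, made up of ocular cicatricial pemphigoid 1, Stevens-Johnson 7, rheumatoid arthritis 4, GVHD 2 and Vogt-Koyanagi-Harada 1; both conditions 4; neither 1; total 68; removals 20.

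**Step 1: reproduce the SAP's counts.**
- Autoimmune by disease: 1 + 7 + 4 + 2 + 1 = 15.
- At least one qualifying condition: 56 + 15 − 4 = 67.
- Total: 67 + 1 = 68.

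The table is internally consistent.

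**Step 2: compare with the 5.1 list.** Taking ocular cicatricial pemphigoid as the protocol's mucous membrane pemphigoid, the listed diseases give 1 + 7 + 4 = 12. The unlisted ones give 2 + 1 = 3, which is 3/15 = 20% of the autoimmune group.

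**Step 3: how many of the three could fail 5.1 on a strict reading?** A subject with an unlisted disease still qualifies through a previous ulcer. Let k be the number of the three with one. The SAP reports 4 subjects with both conditions but not their diseases, so k can be 0, 1, 2 or 3.

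| k | Of the three, failing 5.1 | All subjects failing 5.1 (adding the one with neither) | Eyes meeting 5.1 |
|---|---|---|---|
| 0 | 3 | 4 | 64 |
| 1 | 2 | 3 | 65 |
| 2 | 1 | 2 | 66 |
| 3 | 0 | 1 | 67 |

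On an open reading that admits any autoimmune disease, the three all qualify, and 67 of 68 meet the criterion.

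**Step 4: where in that range?** The documents do not say. As an illustration only, assume that ulcer history among the 15 is unrelated to the particular disease. The chance that all three had an ulcer is then C(4,3)/C(15,3) = 4/455, about 0.9%. The expected number failing is 3 × 11/15 = 2.2, where 11 = 15 − 4. This is an assumption, not a documented fact.

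**Step 5: size of the removal that the SAP actually plans.** It takes out 1 of 68 eyes (1.5%). The events analysed would be 20 or 19, a change of at most 1/20 = 5%. The SAP does not report this subject's arm or outcome.

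**Step 6: set the analysis statements side by side.** The Primary Analysis text includes every randomized eye; the footnote excludes one. Both cannot hold. Keeping the three agrees with the Primary Analysis text.

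**The case against.** **The list in 5.1 may be open.** The lead-in uses a form of 'include', and sections 1.2 and 2.1 are plainly illustrative. This stands as a possible reading. Against it, 1.2 is background and sends the reader to the criteria section for specifics, and the bracketed list in 5.1 carries no qualifier. If the lead-in is open in general, lacking both listed conditions would not by itself make the removed subject ineligible either. The wording is ambiguous; a closed list is not established.

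**The removal rests on a pre-randomization fact.** Such an exclusion need not bias the comparison if it is made without regard to arm or outcome and applied to everyone alike. That is fair, and no results by arm appear in the SAP. It would still be a different analysis set from the one the SAP names, and the SAP does not show that the same check was made against the wording of 5.1 for all subjects.

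**Stronger readings a reader might infer, which the documents do not support:**
- *The three are ineligible.* Not shown, since all three may have had an ulcer.
- *The SAP treats like cases differently.* One broader rule (any autoimmune disease, or a previous ulcer) passes the three and fails the fourth subject. The mismatch is between the SAP's rule and the wording of 5.1, not within the SAP.
- *The three were put in the wrong stratum.* The stratification text contains no disease list, and no subject's assigned stratum is reported. The SAP specifies no stratified log-rank test and no analysis by diagnosis.
- *The three could move the result materially.* Suppose 10 events in 34 eyes per arm, then drop three events from one arm: (10/34)/(7/31) = 1.30, or 0.77 the other way. This assumes that all three lacked an ulcer, shared an arm and lost the device. It also describes dropping eyes that the SAP keeps, using a measure that is not the planned primary one.

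**Conclusion.** The SAP contradicts itself on the primary efficacy set. It removes one randomized eye that its own intent-to-treat statement includes, in a document that already reports 20 removals. The direct effect is limited to 1 of 68 eyes and at most 1 of 20 events.

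Separately, the SAP's autoimmune category is broader than the list in 5.1. Three of 15 subjects have an unlisted disease, and on a strict reading 0 to 3 of them would fail 5.1, leaving 64 to 67 eyes that meet it. The range depends on ulcer history that is not reported by disease.

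Neither bias from the removal, nor mis-stratification, nor any effect of the three on the planned primary result is demonstrated. The conclusion assumes that the 68 implanted eyes were all randomized, as the tissue-ordering procedure implies, and that the two pemphigoid terms mean the same disease.

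**What to change.** 1. Delete the efficacy removal from the SAP's Inclusion Criteria footnote and keep every randomized eye in the primary analysis.
2. Add one sensitivity analysis that drops together all subjects who do not meet 5.1 on facts fixed before randomization (1 to 4 eyes on a strict reading).
3. Report, for the two GVHD subjects and the one Vogt-Koyanagi-Harada subject, whether each had a previous sterile ulcer and which stratum each was assigned. Do not label them as failing 5.1 until the ulcer history is known.
4. Reconcile the wording of Protocol 5.1, 1.2 and 2.1 with the SAP table, so that one definition of autoimmune disease serves eligibility, strata and analysis. The implants date from 2017 to 2020, so any clarification should be marked as made after enrolment.
5. If any analysis uses diagnosis, take the stratum recorded at randomization rather than a later recount.

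The cost is a few lines of text, a look-up of three subjects' existing records and one additional run. No new data collection is needed.
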